7.11. ADDITIONAL SUPPORTING ANALYSES

Additional exploratory analyses that will be conducted to support clinical adoption are defined within the appendices to the Statistical Analysis Plan for OLE Study (ID: SNS-PD-003).

9. APPENDICES

Appendix 1: STEM-PD RCT Schedule of Events

					STEN	M-PD	RCT							
Assessment	Screen Study Center	Baseline 1 Virtual	PC	PRO	Baseline 2 Study Center	PC	PRO	TX 1 Virtual	РС	PRO	TX 2 Virtual	PC	PRO	EOT Study Center
Day	-14 to -1	0 (+/- 3 days)	15 (+/- 1 day)	28 (+/- 1 day)	29 (+/- 3 days	43 (+/- 1 day)	56 (+/- 1 day)	57 (+/- 3 days)	71 (+/- 1 day)	84 (+/- 1 day)	85 (+/- 3 days)	99 (+/- 1 day)	112 (+/- 1 day)	113 (+/- 3 days)
Informed Consent	Х													
Med Hx and ConMed Hx Review	Х	Х			Х									
Review Inclusion/Exclusion	Х				Х									
Pregnancy Test-Urine					Х									
Educational Video and question/answer		Х												
Ear Exam	Х				Х									Х
Height/Weight (height only at screen)	Х				Х									Х
MoCA	Х				Х									Х

					STEN	M-PD	RCT							
Assessment	Screen Study Center	Baseline 1 Virtual	PC	PRO	Baseline 2 Study Center	PC	PRO	TX1 Virtual	PC	PRO	TX2 Virtual	PC	PRO	EOT Study Center
Day	-14 to -1	0 (+/- 3 days)	15 (+/- 1 day)	28 (+/- 1 day)	29 (+/- 3 days	43 (+/- 1 day)	56 (+/- 1 day)	57 (+/- 3 days)	71 (+/- 1 day)	84 (+/- 1 day)	85 (+/- 3 days)	99 (+/- 1 day)	112 (+/- 1 day)	113 (+/- 3 days)
C-SSRS	Х													
UPDRS I					Х									Х
MDS-UPDRS I	X				Х									Х
MDS-NMS		Х			X NMF			Х			Х			X NMF
MDS-UPDRS II		X		Х			Х			X			X	
MDS-UPDRS III (on- state)		X			X			Х			Х			Х
Mini-BESTest					Х									Х
10m TUG					Х									Х
3m TUG & Finger tapping (Encephalog tests)								X*			·			
PDQ-39		Х		Х			Х			X			Х	
Modified Schwab & England					Х									Х
Pro-PD	X				Х									Х

					STEN	M-PD	RCT							
Assessment	Screen Study Center	Baseline 1 Virtual	PC	PRO	Baseline 2 Study Center	PC	PRO	TX1 Virtual	PC	PRO	TX2 Virtual	PC	PRO	EOT Study Center
Day	-14 to -1	0 (+/- 3 days)	15 (+/- 1 day)	28 (+/- 1 day)	29 (+/- 3 days	43 (+/- 1 day)	56 (+/- 1 day)	57 (+/- 3 days)	71 (+/- 1 day)	84 (+/- 1 day)	85 (+/- 3 days)	99 (+/- 1 day)	112 (+/- 1 day)	113 (+/- 3 days)
oSDMT					Х									Х
PDSS-2				Х									Х	
ESS				Х									Х	
PAS				Х									Х	
FACIT-F				Х									Х	
GDS				Х									Х	
Transition Questionnaire							Х							
CGI-I (overall and focused)					Х									Х
UPDRS IV					Х									Х
Zarit Burden Interview					Х									Х
Device Usability Questionnaire														Х
Unpowered Device Fitting					Х									

					STEN	A-PD	RCT							
Assessment	Screen Study Center	Baseline 1 Virtual	PC	PRO	Baseline 2 Study Center	PC	PRO	TX1 Virtual	PC	PRO	TX2 Virtual	PC	PRO	EOT Study Center
Day	-14 to -1	0 (+/- 3 days)	15 (+/- 1 day)	28 (+/- 1 day)	29 (+/- 3 days	43 (+/- 1 day)	56 (+/- 1 day)	57 (+/- 3 days)	71 (+/- 1 day)	84 (+/- 1 day)	85 (+/- 3 days)	99 (+/- 1 day)	112 (+/- 1 day)	113 (+/- 3 days)
Device Randomization and Training					Х									
Device Return														Х
Home Assessment and ePRO Training	Х													
Con Med & AE Review		Х	Х	Х	Х	Х	Х	Х	Х	X	Х	Х	Х	Х
Visit Scheduling and Assessment Review	Х	Х			Х							Х		
Treatment Period	Treatment PeriodX													
X performed twice a day														
X* performed weekly	(* performed weekly													

STEM-PD RCT SAP Appendix 2

This appendix provides instructions for creating the curves to interpret pooled interim analysis to evaluate the percent change in the coefficient of variation in the outcome that may be interpreted as the percent confidence that statistical significance of the outcome will be achieved in the study.

- 1. Determine baseline value of (SD / \overline{x}) : $(SD / \overline{x})_0$
- 2. Pick a percent increase in $(SD / \overline{x})_0$
- 3. Calculate $(SD / \overline{x})_1$: Multiply $(SD / \overline{x})_0$ by (1 + (percent increase / 100))

 $[(n-1)((SD / \overline{x})_0)^2]$

4. Calculate $\chi^2 : \chi^2 =$

 $((SD / \bar{x})_1)^2$

- 5. Calculate right tailed probability, p, based on χ^2 and (n-1) degrees of freedom.
- 6. Calculate the measure of confidence: %Confidence = (1 p)

where:

SD = Standard Deviation

 $\overline{\mathbf{x}} = \text{mean}$

n = number of subjects

p = right tailed probability

 $\chi 2 = Chi$ Square statistic

Subscript 0 denotes baseline

Subscript 1 denotes end of treatment

CONFIDENTIAL-Page 42 of 66

Interim Analysis Confidence Tables

Alpha = 0.05

n	5% increas	e in stdev	χ^2	р	% Confidence
	(s / x̄) ₀	(s / x̄)1			
5	0.05	0.0525	3.6281	0.5413	45.8667
6	0.05	0.0525	4.5351	0.5248	47.5195
7	0.05	0.0525	5.4422	0.5115	48.8473
8	0.05	0.0525	6.3492	0.5004	49.9616
9	0.05	0.0525	7.2562	0.4907	50.9256
10	0.05	0.0525	8.1633	0.4822	51.7781
11	0.05	0.0525	9.0703	0.4746	52.5446
12	0.05	0.0525	9.9773	0.4676	53.2428
13	0.05	0.0525	10.8844	0.4611	53.8855
14	0.05	0.0525	11.7914	0.4552	54.4820
15	0.05	0.0525	12.6984	0.4496	55.0396
16	0.05	0.0525	13.6054	0.4444	55.5639
17	0.05	0.0525	14.5125	0.4394	56.0593
18	0.05	0.0525	15.4195	0.4347	56.5293
19	0.05	0.0525	16.3265	0.4302	56.9770
20	0.05	0.0525	17.2336	0.4260	57.4048
21	0.05	0.0525	18.1406	0.4219	57.8147
22	0.05	0.0525	19.0476	0.4179	58.2085

23	0.05	0.0525	19.9546	0.4141	58.5877
24	0.05	0.0525	20.8617	0.4105	58.9534
25	0.05	0.0525	21.7687	0.4069	59.3070
26	0.05	0.0525	22.6757	0.4035	59.6492
27	0.05	0.0525	23.5828	0.4002	59.9810
28	0.05	0.0525	24.4898	0.3970	60.3031
29	0.05	0.0525	25.3968	0.3938	60.6162
30	0.05	0.0525	26.3039	0.3908	60.9209
31	0.05	0.0525	27.2109	0.3878	61.2177
32	0.05	0.0525	28.1179	0.3849	61.5071
33	0.05	0.0525	29.0249	0.3821	61.7896
34	0.05	0.0525	29.9320	0.3793	62.0655
35	0.05	0.0525	30.8390	0.3766	62.3353
36	0.05	0.0525	31.7460	0.3740	62.5992
37	0.05	0.0525	32.6531	0.3714	62.8575
38	0.05	0.0525	33.5601	0.3689	63.1105
39	0.05	0.0525	34.4671	0.3664	63.3585
40	0.05	0.0525	35.3741	0.3640	63.6017
41	0.05	0.0525	36.2812	0.3616	63.8403
42	0.05	0.0525	37.1882	0.3593	64.0746
43	0.05	0.0525	38.0952	0.3570	64.3047
44	0.05	0.0525	39.0023	0.3547	64.5308
45	0.05	0.0525	39.9093	0.3525	64.7530

46	0.05	0.0525	40.8163	0.3503	64.9716
47	0.05	0.0525	41.7234	0.3481	65.1866
48	0.05	0.0525	42.6304	0.3460	65.3981
49	0.05	0.0525	43.5374	0.3439	65.6064
50	0.05	0.0525	44.4444	0.3419	65.8116
51	0.05	0.0525	45.3515	0.3399	66.0136
52	0.05	0.0525	46.2585	0.3379	66.2127
53	0.05	0.0525	47.1655	0.3359	66.4090
54	0.05	0.0525	48.0726	0.3340	66.6025
55	0.05	0.0525	48.9796	0.3321	66.7933
56	0.05	0.0525	49.8866	0.3302	66.9815
57	0.05	0.0525	50.7937	0.3283	67.1672
58	0.05	0.0525	51.7007	0.3265	67.3505
59	0.05	0.0525	52.6077	0.3247	67.5314
60	0.05	0.0525	53.5147	0.3229	67.7101
61	0.05	0.0525	54.4218	0.3211	67.8865
62	0.05	0.0525	55.3288	0.3194	68.0607
63	0.05	0.0525	56.2358	0.3177	68.2328
64	0.05	0.0525	57.1429	0.3160	68.4029
65	0.05	0.0525	58.0499	0.3143	68.5710
66	0.05	0.0525	58.9569	0.3126	68.7371
67	0.05	0.0525	59.8639	0.3110	68.9014
68	0.05	0.0525	60.7710	0.3094	69.0638

69	0.05	0.0525	61.6780	0.3078	69.2244
70	0.05	0.0525	62.5850	0.3062	69.3832
71	0.05	0.0525	63.4921	0.3046	69.5403
72	0.05	0.0525	64.3991	0.3030	69.6958
73	0.05	0.0525	65.3061	0.3015	69.8496
74	0.05	0.0525	66.2132	0.3000	70.0018
75	0.05	0.0525	67.1202	0.2985	70.1524

n	10% increa	ase in stdev	2	n	%
n	(s / x̄) ₀	(s / x̄) ₁	χ^2	р	Confidence
5	0.05	0.055	3.3058	0.4920	50.8016
6	0.05	0.055	4.1322	0.4695	53.0539
7	0.05	0.055	4.9587	0.4509	54.9124
8	0.05	0.055	5.7851	0.4349	56.5052
9	0.05	0.055	6.6116	0.4209	57.9061
10	0.05	0.055	7.4380	0.4084	59.1614
11	0.05	0.055	8.2645	0.3970	60.3022
12	0.05	0.055	9.0909	0.3865	61.3501
13	0.05	0.055	9.9174	0.3768	62.3211
14	0.05	0.055	10.7438	0.3677	63.2270
15	0.05	0.055	11.5702	0.3592	64.0772
16	0.05	0.055	12.3967	0.3512	64.8788
17	0.05	0.055	13.2231	0.3436	65.6378
18	0.05	0.055	14.0496	0.3364	66.3589
19	0.05	0.055	14.8760	0.3295	67.0461
20	0.05	0.055	15.7025	0.3230	67.7027
21	0.05	0.055	16.5289	0.3167	68.3316
22	0.05	0.055	17.3554	0.3106	68.9352
23	0.05	0.055	18.1818	0.3048	69.5156
24	0.05	0.055	19.0083	0.2993	70.0745

CONFIDENTIAL-Page 47 of 66

25	0.05	0.055	19.8347	0.2939	70.6136
26	0.05	0.055	20.6612	0.2887	71.1343
27	0.05	0.055	21.4876	0.2836	71.6378
28	0.05	0.055	22.3140	0.2787	72.1253
29	0.05	0.055	23.1405	0.2740	72.5977
30	0.05	0.055	23.9669	0.2694	73.0560
31	0.05	0.055	24.7934	0.2650	73.5009
32	0.05	0.055	25.6198	0.2607	73.9333
33	0.05	0.055	26.4463	0.2565	74.3536
34	0.05	0.055	27.2727	0.2524	74.7627
35	0.05	0.055	28.0992	0.2484	75.1611
36	0.05	0.055	28.9256	0.2445	75.5491
37	0.05	0.055	29.7521	0.2407	75.9275
38	0.05	0.055	30.5785	0.2370	76.2965
39	0.05	0.055	31.4050	0.2334	76.6566
40	0.05	0.055	32.2314	0.2299	77.0082
41	0.05	0.055	33.0579	0.2265	77.3517
42	0.05	0.055	33.8843	0.2231	77.6873
43	0.05	0.055	34.7107	0.2198	78.0154
44	0.05	0.055	35.5372	0.2166	78.3362
45	0.05	0.055	36.3636	0.2135	78.6501
46	0.05	0.055	37.1901	0.2104	78.9573
47	0.05	0.055	38.0165	0.2074	79.2580

48	0.05	0.055	38.8430	0.2045	79.5524
49	0.05	0.055	39.6694	0.2016	79.8409
50	0.05	0.055	40.4959	0.1988	80.1235
51	0.05	0.055	41.3223	0.1960	80.4005
52	0.05	0.055	42.1488	0.1933	80.6721
53	0.05	0.055	42.9752	0.1906	80.9383
54	0.05	0.055	43.8017	0.1880	81.1995
55	0.05	0.055	44.6281	0.1854	81.4557
56	0.05	0.055	45.4545	0.1829	81.7071
57	0.05	0.055	46.2810	0.1805	81.9539
58	0.05	0.055	47.1074	0.1780	82.1961
59	0.05	0.055	47.9339	0.1757	82.4339
60	0.05	0.055	48.7603	0.1733	82.6674
61	0.05	0.055	49.5868	0.1710	82.8968
62	0.05	0.055	50.4132	0.1688	83.1221
63	0.05	0.055	51.2397	0.1666	83.3435
64	0.05	0.055	52.0661	0.1644	83.5610
65	0.05	0.055	52.8926	0.1623	83.7749
66	0.05	0.055	53.7190	0.1601	83.9850
67	0.05	0.055	54.5455	0.1581	84.1917
68	0.05	0.055	55.3719	0.1561	84.3948
69	0.05	0.055	56.1983	0.1541	84.5946
70	0.05	0.055	57.0248	0.1521	84.7911

71	0.05	0.055	57.8512	0.1502	84.9844
72	0.05	0.055	58.6777	0.1483	85.1746
73	0.05	0.055	59.5041	0.1464	85.3617
74	0.05	0.055	60.3306	0.1445	85.5458
75	0.05	0.055	61.1570	0.1427	85.7269

	15% increase in stde		~ ²	_	%
n	(s / x̄) ₀	(s / x̄) ₁	χ^2	р	Confidence
5	0.05	0.0575	3.0246	0.4463	55.3721
6	0.05	0.0575	3.7807	0.4186	58.1399
7	0.05	0.0575	4.5369	0.3956	60.4427
8	0.05	0.0575	5.2930	0.3757	62.4254
9	0.05	0.0575	6.0491	0.3583	64.1726
10	0.05	0.0575	6.8053	0.3426	65.7383
11	0.05	0.0575	7.5614	0.3284	67.1589
12	0.05	0.0575	8.3176	0.3154	68.4605
13	0.05	0.0575	9.0737	0.3034	69.6621
14	0.05	0.0575	9.8299	0.2922	70.7784
15	0.05	0.0575	10.5860	0.2818	71.8208
16	0.05	0.0575	11.3422	0.2720	72.7984
17	0.05	0.0575	12.0983	0.2628	73.7186
18	0.05	0.0575	12.8544	0.2541	74.5874
19	0.05	0.0575	13.6106	0.2459	75.4101
20	0.05	0.0575	14.3667	0.2381	76.1908
21	0.05	0.0575	15.1229	0.2307	76.9334
22	0.05	0.0575	15.8790	0.2236	77.6410
23	0.05	0.0575	16.6352	0.2168	78.3163
24	0.05	0.0575	17.3913	0.2104	78.9619

25	0.05	0.0575	18.1474	0.2042	79.5798
26	0.05	0.0575	18.9036	0.1983	80.1720
27	0.05	0.0575	19.6597	0.1926	80.7401
28	0.05	0.0575	20.4159	0.1871	81.2858
29	0.05	0.0575	21.1720	0.1819	81.8104
30	0.05	0.0575	21.9282	0.1768	82.3152
31	0.05	0.0575	22.6843	0.1720	82.8012
32	0.05	0.0575	23.4405	0.1673	83.2696
33	0.05	0.0575	24.1966	0.1628	83.7213
34	0.05	0.0575	24.9527	0.1584	84.1571
35	0.05	0.0575	25.7089	0.1542	84.5780
36	0.05	0.0575	26.4650	0.1502	84.9845
37	0.05	0.0575	27.2212	0.1462	85.3775
38	0.05	0.0575	27.9773	0.1424	85.7575
39	0.05	0.0575	28.7335	0.1387	86.1252
40	0.05	0.0575	29.4896	0.1352	86.4811
41	0.05	0.0575	30.2457	0.1317	86.8257
42	0.05	0.0575	31.0019	0.1284	87.1595
43	0.05	0.0575	31.7580	0.1252	87.4831
44	0.05	0.0575	32.5142	0.1220	87.7967
45	0.05	0.0575	33.2703	0.1190	88.1009
46	0.05	0.0575	34.0265	0.1160	88.3959
47	0.05	0.0575	34.7826	0.1132	88.6822

48	0.05	0.0575	35.5388	0.1104	88.9601
49	0.05	0.0575	36.2949	0.1077	89.2299
50	0.05	0.0575	37.0510	0.1051	89.4920
51	0.05	0.0575	37.8072	0.1025	89.7465
52	0.05	0.0575	38.5633	0.1001	89.9938
53	0.05	0.0575	39.3195	0.0977	90.2342
54	0.05	0.0575	40.0756	0.0953	90.4679
55	0.05	0.0575	40.8318	0.0930	90.6950
56	0.05	0.0575	41.5879	0.0908	90.9160
57	0.05	0.0575	42.3440	0.0887	91.1309
58	0.05	0.0575	43.1002	0.0866	91.3399
59	0.05	0.0575	43.8563	0.0846	91.5434
60	0.05	0.0575	44.6125	0.0826	91.7413
61	0.05	0.0575	45.3686	0.0807	91.9340
62	0.05	0.0575	46.1248	0.0788	92.1217
63	0.05	0.0575	46.8809	0.0770	92.3043
64	0.05	0.0575	47.6371	0.0752	92.4822
65	0.05	0.0575	48.3932	0.0734	92.6555
66	0.05	0.0575	49.1493	0.0718	92.8243
67	0.05	0.0575	49.9055	0.0701	92.9887
68	0.05	0.0575	50.6616	0.0685	93.1489
69	0.05	0.0575	51.4178	0.0669	93.3051
70	0.05	0.0575	52.1739	0.0654	93.4573

71	0.05	0.0575	52.9301	0.0639	93.6056
72	0.05	0.0575	53.6862	0.0625	93.7502
73	0.05	0.0575	54.4423	0.0611	93.8912
74	0.05	0.0575	55.1985	0.0597	94.0287
75	0.05	0.0575	55.9546	0.0584	94.1627

onfidence 59.5675
59.5675
62.7595
65.4133
67.6908
69.6877
71.4660
73.0679
74.5240
75.8569
77.0842
78.2197
79.2745
80.2576
81.1766
82.0379
82.8470
83.6085
84.3264
85.0044
85.6455

CONFIDENTIAL-Page 55 of 66

25	0.05	0.06	16.6667	0.1375	86.2526
26	0.05	0.06	17.3611	0.1317	86.8281
27	0.05	0.06	18.0556	0.1263	87.3743
28	0.05	0.06	18.7500	0.1211	87.8931
29	0.05	0.06	19.4444	0.1161	88.3864
30	0.05	0.06	20.1389	0.1114	88.8557
31	0.05	0.06	20.8333	0.1070	89.3027
32	0.05	0.06	21.5278	0.1027	89.7286
33	0.05	0.06	22.2222	0.0987	90.1348
34	0.05	0.06	22.9167	0.0948	90.5224
35	0.05	0.06	23.6111	0.0911	90.8924
36	0.05	0.06	24.3056	0.0875	91.2459
37	0.05	0.06	25.0000	0.0842	91.5837
38	0.05	0.06	25.6944	0.0809	91.9067
39	0.05	0.06	26.3889	0.0778	92.2156
40	0.05	0.06	27.0833	0.0749	92.5113
41	0.05	0.06	27.7778	0.0721	92.7944
42	0.05	0.06	28.4722	0.0693	93.0656
43	0.05	0.06	29.1667	0.0667	93.3254
44	0.05	0.06	29.8611	0.0643	93.5743
45	0.05	0.06	30.5556	0.0619	93.8130
46	0.05	0.06	31.2500	0.0596	94.0419
47	0.05	0.06	31.9444	0.0574	94.2615

48	0.05	0.06	32.6389	0.0553	94.4723
49	0.05	0.06	33.3333	0.0533	94.6745
50	0.05	0.06	34.0278	0.0513	94.8687
51	0.05	0.06	34.7222	0.0494	95.0552
52	0.05	0.06	35.4167	0.0477	95.2343
53	0.05	0.06	36.1111	0.0459	95.4063
54	0.05	0.06	36.8056	0.0443	95.5717
55	0.05	0.06	37.5000	0.0427	95.7306
56	0.05	0.06	38.1944	0.0412	95.8834
57	0.05	0.06	38.8889	0.0397	96.0303
58	0.05	0.06	39.5833	0.0383	96.1716
59	0.05	0.06	40.2778	0.0369	96.3075
60	0.05	0.06	40.9722	0.0356	96.4383
61	0.05	0.06	41.6667	0.0344	96.5641
62	0.05	0.06	42.3611	0.0331	96.6851
63	0.05	0.06	43.0556	0.0320	96.8016
64	0.05	0.06	43.7500	0.0309	96.9138
65	0.05	0.06	44.4444	0.0298	97.0218
66	0.05	0.06	45.1389	0.0287	97.1258
67	0.05	0.06	45.8333	0.0277	97.2259
68	0.05	0.06	46.5278	0.0268	97.3224
69	0.05	0.06	47.2222	0.0258	97.4153
70	0.05	0.06	47.9167	0.0250	97.5048

71	0.05	0.06	48.6111	0.0241	97.5910
72	0.05	0.06	49.3056	0.0233	97.6741
73	0.05	0.06	50.0000	0.0225	97.7542
74	0.05	0.06	50.6944	0.0217	97.8314
75	0.05	0.06	51.3889	0.0209	97.9058

	25% increase in stdev		2		%
n	(s / x̄) ₀	(s / x̄) ₁	χ^2	р	Confidence
5	0.05	0.0625	2.5600	0.3661	63.3925
6	0.05	0.0625	3.2000	0.3308	66.9183
7	0.05	0.0625	3.8400	0.3017	69.8318
8	0.05	0.0625	4.4800	0.2769	72.3124
9	0.05	0.0625	5.1200	0.2553	74.4677
10	0.05	0.0625	5.7600	0.2363	76.3677
11	0.05	0.0625	6.4000	0.2194	78.0613
12	0.05	0.0625	7.0400	0.2042	79.5835
13	0.05	0.0625	7.6800	0.1904	80.9611
14	0.05	0.0625	8.3200	0.1779	82.2146
15	0.05	0.0625	8.9600	0.1664	83.3604
16	0.05	0.0625	9.6000	0.1559	84.4119
17	0.05	0.0625	10.2400	0.1462	85.3798
18	0.05	0.0625	10.8800	0.1373	86.2734
19	0.05	0.0625	11.5200	0.1290	87.1003
20	0.05	0.0625	12.1600	0.1213	87.8673
21	0.05	0.0625	12.8000	0.1142	88.5799
22	0.05	0.0625	13.4400	0.1076	89.2432
23	0.05	0.0625	14.0800	0.1014	89.8616
24	0.05	0.0625	14.7200	0.0956	90.4387

25	0.05	0.0625	15.3600	0.0902	90.9782
26	0.05	0.0625	16.0000	0.0852	91.4829
27	0.05	0.0625	16.6400	0.0804	91.9556
28	0.05	0.0625	17.2800	0.0760	92.3988
29	0.05	0.0625	17.9200	0.0719	92.8146
30	0.05	0.0625	18.5600	0.0679	93.2051
31	0.05	0.0625	19.2000	0.0643	93.5721
32	0.05	0.0625	19.8400	0.0608	93.9172
33	0.05	0.0625	20.4800	0.0576	94.2420
34	0.05	0.0625	21.1200	0.0545	94.5477
35	0.05	0.0625	21.7600	0.0516	94.8358
36	0.05	0.0625	22.4000	0.0489	95.1073
37	0.05	0.0625	23.0400	0.0464	95.3634
38	0.05	0.0625	23.6800	0.0440	95.6050
39	0.05	0.0625	24.3200	0.0417	95.8330
40	0.05	0.0625	24.9600	0.0395	96.0483
41	0.05	0.0625	25.6000	0.0375	96.2517
42	0.05	0.0625	26.2400	0.0356	96.4439
43	0.05	0.0625	26.8800	0.0337	96.6256
44	0.05	0.0625	27.5200	0.0320	96.7975
45	0.05	0.0625	28.1600	0.0304	96.9600
46	0.05	0.0625	28.8000	0.0289	97.1138
47	0.05	0.0625	29.4400	0.0274	97.2594

48	0.05	0.0625	30.0800	0.0260	97.3972
49	0.05	0.0625	30.7200	0.0247	97.5277
50	0.05	0.0625	31.3600	0.0235	97.6513
51	0.05	0.0625	32.0000	0.0223	97.7685
52	0.05	0.0625	32.6400	0.0212	97.8795
53	0.05	0.0625	33.2800	0.0202	97.9847
54	0.05	0.0625	33.9200	0.0192	98.0844
55	0.05	0.0625	34.5600	0.0182	98.1790
56	0.05	0.0625	35.2000	0.0173	98.2687
57	0.05	0.0625	35.8400	0.0165	98.3538
58	0.05	0.0625	36.4800	0.0157	98.4346
59	0.05	0.0625	37.1200	0.0149	98.5112
60	0.05	0.0625	37.7600	0.0142	98.5839
61	0.05	0.0625	38.4000	0.0135	98.6530
62	0.05	0.0625	39.0400	0.0128	98.7185
63	0.05	0.0625	39.6800	0.0122	98.7808
64	0.05	0.0625	40.3200	0.0116	98.8399
65	0.05	0.0625	40.9600	0.0110	98.8961
66	0.05	0.0625	41.6000	0.0105	98.9494
67	0.05	0.0625	42.2400	0.0100	99.0001
68	0.05	0.0625	42.8800	0.0095	99.0482
69	0.05	0.0625	43.5200	0.0091	99.0940
70	0.05	0.0625	44.1600	0.0086	99.1375

71	0.05	0.0625	44.8000	0.0082	99.1788
72	0.05	0.0625	45.4400	0.0078	99.2181
73	0.05	0.0625	46.0800	0.0074	99.2555
74	0.05	0.0625	46.7200	0.0071	99.2910
75	0.05	0.0625	47.3600	0.0068	99.3248

	30% increa	ase in stdev	2		%
n	(s / x̄) ₀	(s / x̄) ₁	χ^2	р	Confidence
5	0.05	0.065	2.3669	0.3314	66.8624
6	0.05	0.065	2.9586	0.2936	70.6372
7	0.05	0.065	3.5503	0.2627	73.7266
8	0.05	0.065	4.1420	0.2367	76.3283
9	0.05	0.065	4.7337	0.2144	78.5620
10	0.05	0.065	5.3254	0.1949	80.5066
11	0.05	0.065	5.9172	0.1778	82.2174
12	0.05	0.065	6.5089	0.1627	83.7349
13	0.05	0.065	7.1006	0.1491	85.0895
14	0.05	0.065	7.6923	0.1369	86.3052
15	0.05	0.065	8.2840	0.1260	87.4010
16	0.05	0.065	8.8757	0.1161	88.3924
17	0.05	0.065	9.4675	0.1071	89.2922
18	0.05	0.065	10.0592	0.0989	90.1111
19	0.05	0.065	10.6509	0.0914	90.8580
20	0.05	0.065	11.2426	0.0846	91.5408
21	0.05	0.065	11.8343	0.0783	92.1661
22	0.05	0.065	12.4260	0.0726	92.7396
23	0.05	0.065	13.0178	0.0673	93.2665
24	0.05	0.065	13.6095	0.0625	93.7512

CONFIDENTIAL-Page 63 of 66

25	5	0.05	0.065	14.2012	0.0580	94.1975
26	6	0.05	0.065	14.7929	0.0539	94.6090
27	7	0.05	0.065	15.3846	0.0501	94.9888
28	8	0.05	0.065	15.9763	0.0466	95.3397
29	9	0.05	0.065	16.5680	0.0434	95.6640
30	C	0.05	0.065	17.1598	0.0404	95.9642
31	1	0.05	0.065	17.7515	0.0376	96.2420
32	2	0.05	0.065	18.3432	0.0350	96.4995
33	3	0.05	0.065	18.9349	0.0326	96.7382
34	4	0.05	0.065	19.5266	0.0304	96.9596
35	5	0.05	0.065	20.1183	0.0283	97.1651
36	6	0.05	0.065	20.7101	0.0264	97.3560
37	7	0.05	0.065	21.3018	0.0247	97.5333
38	8	0.05	0.065	21.8935	0.0230	97.6982
39	9	0.05	0.065	22.4852	0.0215	97.8514
4(0	0.05	0.065	23.0769	0.0201	97.9940
41	1	0.05	0.065	23.6686	0.0187	98.1267
42	2	0.05	0.065	24.2604	0.0175	98.2502
43	3	0.05	0.065	24.8521	0.0163	98.3653
44	4	0.05	0.065	25.4438	0.0153	98.4725
43	5	0.05	0.065	26.0355	0.0143	98.5724
46	5	0.05	0.065	26.6272	0.0133	98.6655
47	7	0.05	0.065	27.2189	0.0125	98.7523

48	0.05	0.065	27.8107	0.0117	98.8332
49	0.05	0.065	28.4024	0.0109	98.9088
50	0.05	0.065	28.9941	0.0102	98.9793
51	0.05	0.065	29.5858	0.0095	99.0450
52	0.05	0.065	30.1775	0.0089	99.1065
53	0.05	0.065	30.7692	0.0084	99.1638
54	0.05	0.065	31.3609	0.0078	99.2174
55	0.05	0.065	31.9527	0.0073	99.2674
56	0.05	0.065	32.5444	0.0069	99.3142
57	0.05	0.065	33.1361	0.0064	99.3578
58	0.05	0.065	33.7278	0.0060	99.3987
59	0.05	0.065	34.3195	0.0056	99.4368
60	0.05	0.065	34.9112	0.0053	99.4725
61	0.05	0.065	35.5030	0.0049	99.5059
62	0.05	0.065	36.0947	0.0046	99.5371
63	0.05	0.065	36.6864	0.0043	99.5663
64	0.05	0.065	37.2781	0.0041	99.5936
65	0.05	0.065	37.8698	0.0038	99.6192
66	0.05	0.065	38.4615	0.0036	99.6431
67	0.05	0.065	39.0533	0.0033	99.6655
68	0.05	0.065	39.6450	0.0031	99.6865
69	0.05	0.065	40.2367	0.0029	99.7061
70	0.05	0.065	40.8284	0.0028	99.7244

71	0.05	0.065	41.4201	0.0026	99.7416
72	0.05	0.065	42.0118	0.0024	99.7577
73	0.05	0.065	42.6036	0.0023	99.7728
74	0.05	0.065	43.1953	0.0021	99.7870
75	0.05	0.065	43.7870	0.0020	99.8002

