The interim analysis utilizes as its metric the ratio of the sample standard deviation divided by the sample mean. This metric is calculated at baseline and post treatment. The difference between these two values is divided by its baseline value as depicted in the following formula:

where:

 $\%\Delta_{SD/X}$ = the percent change in the coefficient of variation in the outcome (e.g., MDS-NMS total) score between baseline and post treatment which may be interpreted as the percent confidence that statistical significance of the outcome will be achieved in the study

 $X_{baseline}$ = the mean of the outcome scores at baseline – for outcomes collected at both baseline visits, the $X_{baseline}$ will be the mean of the study participants' baseline scores, BL_{ave}

 $SD_{baseline}$ = the standard deviation of the outcome scores at baseline – for outcomes collected at both baseline visits, the $SD_{baseline}$ will be the standard deviation of the study participants' BL_{ave} scores

 X_{post} = the mean of the outcome scores at the end of the treatment period

 SD_{post} = the standard deviation of the outcome scores at the end of treatment

For each noncomparative interim analysis, two cohorts may be evaluated. The first will be the cohort for which end of treatment data exist (i.e., data collected at either the end of the scheduled treatment period or an early termination visit). The second cohort will only evaluate data from participants that completed the visit at the end of the regularly scheduled treatment period and will exclude those with early termination from the study.

The figure below provides sample sizes that would be required to obtain percent confidence of meeting the primary endpoint assuming a change in the standard deviation of scores divided by the mean metric between the baseline and the end of treatment assessment.

[figure not shown]

Figure 1. Estimated percent confidence of achieving statistical significance in the primary endpoint according to pooled interim data collected from both treatment arms. Sample sizes that would be required to obtain percent confidence of meeting the primary endpoint assuming a change in the standard deviation of scores divided by the mean. For example, if a difference of 10% of the SD/x metric is observed in a sample of 50 participants, the metric would provide 80% confidence that the endpoint will be statistically significant at the end of the study.

CONFIDENTIAL-Page 11 of 66

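### RCT SAP Appendix 2 names the right-tailed chi-square probability, but its tables and the Figure 1 example use the left tail, so the steps as written return the complement of the intended confidence.

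*SAP*

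**What the plan says.** Section 5 of the RCT SAP (Non-Comparative Interim Analysis) allows an optional analysis of pooled, blinded data while the RCT is running. Its metric is the percent change in SD/mean between baseline and end of treatment, which the SAP reads as confidence that an endpoint will reach significance. The legend of Figure 1 gives a worked example: "if a difference of 10% of the SD/x metric is observed in a sample of 50 participants, the metric would provide 80% confidence".

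Appendix 2 of the RCT SAP gives the recipe:
- Steps 1 to 3 take the baseline SD/mean and multiply it by one plus the percent increase over 100.
- Step 4 forms a chi-square statistic from n - 1 and the two squared ratios.
- Step 5 says "Calculate right tailed probability, p, based on" that statistic with n - 1 degrees of freedom.
- Step 6 sets the confidence to one minus p.
- The legend below the steps again states "p = right tailed probability".

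Six tables follow, for increases of 5, 10, 15, 20, 25 and 30% and n from 5 to 75. For n = 50 and 10%, the chi-square, p and confidence are printed as "40.4959 0.1988 80.1235". For n = 5 and 5% they are "3.6281 0.5413 45.8667".

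**The concern.** The recipe and the tables cannot both be right about the tail. With 49 degrees of freedom, a chi-square of 40.4959 lies below its mean, so its right-tailed probability must be well above one half. The table prints p = 0.1988. If the tables carry the intended values, an analyst who follows steps 5 and 6 reports the complement of each one, and a larger change in SD/mean shows as lower confidence.

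What is at stake is the reading of the interim result. Section 5 sends it to the Independent Medical Monitor and the Safety Medical Monitor, and allows results suggesting futility to be considered when the Independent Medical Monitor recommends proceeding or pausing. The same section gives fundraising as the purpose of the metric. A reversed value would mislead in either use.

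**Working it through.** **Inputs.** Steps 3 to 6, the legend and the tables of RCT SAP Appendix 2; the Figure 1 example in RCT SAP section 5.

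**Formula.** The end-of-treatment ratio is the baseline ratio times (1 + d), where d is the increase as a fraction. The baseline ratio therefore cancels in step 4:

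chi-square = (n - 1) / (1 + d)², with n - 1 degrees of freedom.

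The fraction in step 4 is broken in the extracted text, but the printed chi-square values confirm this orientation.

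**Reproducing the SAP's own example (n = 50, 10%).**
- chi-square = 49 / 1.1² = 49 / 1.21 = 40.4959, as printed.
- Left tail on 49 df = 0.1988, the printed p. One minus this is 80.12%, the printed confidence and the 80% of Figure 1.
- Right tail on 49 df = 0.8012. Steps 5 and 6 as written give 1 - 0.8012 = 19.88%.

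**A row that can be checked by hand (n = 5, 5%).**
- chi-square = 4 / 1.05² = 4 / 1.1025 = 3.6281, as printed.
- With 4 df the right tail has the closed form exp(-x/2)(1 + x/2) = 0.16299 × 2.81405 = 0.4587.
- Left tail = 1 - 0.4587 = 0.5413, the printed p. Confidence by the table is 45.87%; by the steps it is 54.13%.

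**All six tables.** Twenty-one complete rows were recomputed, including n = 50 and n = 75 in each table. In all of them the printed p equals the left tail and the printed confidence equals one minus it. In the 20% table the p column is not legible for n = 5 to 24. The confidences printed there for n = 5 (59.5675) and n = 24 (85.6455) also equal one minus the left tail.

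**Steps against tables at n = 50.**

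| Increase in SD/mean | Chi-square | Table confidence | Steps as written |
|---|---|---|---|
| 5% | 44.4444 | 65.8% | 34.2% |
| 10% | 40.4959 | 80.1% | 19.9% |
| 15% | 37.0510 | 89.5% | 10.5% |
| 20% | 34.0278 | 94.9% | 5.1% |
| 25% | 31.3600 | 97.7% | 2.3% |
| 30% | 28.9941 | 99.0% | 1.0% |

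The table column rises with the change and the steps column falls. At n = 75 and 30% the two values are 99.8% and 0.2%.

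**Alternative explanations tried (n = 50, 10%).** Inverting the ratio and keeping the right tail gives p = 0.1490 and 85.10%. Using n instead of n - 1 degrees of freedom gives a right tail of 0.829. Neither reproduces 0.1988 and 80.12%; only the change of tail does.

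**A value between the tables.** For n = 50 and 8%, chi-square = 49 / 1.08² = 49 / 1.1664 = 42.0096, with left tail 0.250 and right tail 0.750. The tables' method gives 75.0%; the steps give 25.0%.

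**The case against.** The strongest reply is that no printed number has been shown to be wrong. The tables agree with each other and with the Figure 1 example; only the name of the tail conflicts. An analyst who compares one computed value with one table row sees the mismatch at once. This stands: the fault is in the written rule, not in the tabulated results, and the SAP contains the means to detect it. It does not remove the point, because the rule is stated twice in the same wrong form and a program checked only against the written steps would pass.

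The second reply is that the consequence is conditional throughout. The analysis may never be run; it is pooled and blinded; section 5 sets no numerical futility threshold; and high values are not a reason to stop early. This also stands.

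A reader might infer that an interim of any size beyond the tables, up to the roughly 166 expected completers, would have to be computed from the steps. The documents do not establish that. The interim takes place while the RCT is ongoing, so the number completing the whole RCT is not a realistic interim size. Figure 1 is also not visible in the text reviewed, so some values outside the tables may be readable from its curves. What can be said is that the tables stop at n = 75 and cover six percentages, and that the steps are the SAP's stated method for creating the curves.

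**Conclusion.** The contradiction is certain and follows from the SAP alone. Step 5 and the legend name the right tail, while every table row checked and the Figure 1 example use the left. Taken literally, the steps return 100% minus the intended value; in the SAP's own example that is 19.9% instead of 80.1%.

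The practical consequence is conditional. It arises if the optional interim is run and either programmed from the steps or needed at n above 75 or at a percentage other than 5, 10, 15, 20, 25 or 30%. In that case a stronger signal would look weaker to a monitor who may weigh futility. A reader might go further and conclude that a favourable interim would be taken as futile, or that the trial's inference is compromised. The documents do not support either conclusion: no futility threshold is set, the tables would expose the mismatch, and no alpha level, sample size, or primary or secondary test depends on this calculation.

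The verdict assumes that the tables and Figure 1 carry the intended values, since they agree with each other. It does not address whether the metric measures the chance of trial success, which is a separate question.

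**What to change.** If the metric is kept, make one of two equivalent changes:
- replace the right-tailed wording with left-tailed (cumulative) in both step 5 and the legend, leaving step 6 as it is; or
- keep the right tail in both places and redefine the confidence in step 6 as p, expressed as a percentage. The p column of the tables would then need relabelling or replacing, because it prints the left tail.

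The first is simpler, since the tables stay as they are. Correcting step 5 alone is not enough, because the legend would then contradict it. In either case, require the program to reproduce the n = 50, 10% entry (80.12%) before any interim result is released.

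The cost is an edit of a few words in the SAP appendix and one program check. No design element, data collection or confirmatory analysis changes.
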